**Table 1. SEEK Training Strategies**

SEEK MOC-4	Independent Online (IND)
Eligible for MOC 4 and CME credits	Eligible for MOC CME credits
Engage in SEEK QI project – PDSA cycle	N/A
Participate in four 1-hr. webinars	N/A
View SEEK training videos (2.5 hours)	View SEEK training videos
Pass SEEK Post-test	Pass SEEK Post-test
Participate in 3 one-hour consultation sessions	Participate in 3 one-hour consultation sessions

**Facilitation of Service Delivery.** SEEKonline is software to efficiently implement SEEK via a secure web-based system interfacing with a practice's EHR. SEEKonline has been developed and is currently being beta tested. Its effectiveness in improving implementation outcomes compared to the Traditional paper-and-pencil approach has yet to be examined. Data are stored in a Microsoft SQL Server Database, in an isolated, secure, private cloud environment, behind a fully HIPAA-certified network security device. SEEKonline enables parents to privately complete the SEEK PQ before a child's checkup. Responses are available to PCPs

**Table 2. SEEK Intervention Strategies**

SEEK online	Traditional
Parent completes SEEK PQ online	Parent completes SEEK PQ with paper and pencil
SEEK PQ adds probes for positive screens	Probes are conducted during the visit, orally
PCP has parent's info at start of visit	PCP has parent's info at start of visit
Electronic decision support for PCP	PCP has SEEK algorithms as Word documents
Auto documentation	PCP needs to document
Info sent to private Care portal	N/A
Parent Handouts readily printed	Parent Handouts need to be printed in advance
Information readily integrated into EHR	Information less readily integrated into EHR
Aggregate data readily available for QI projects	Aggregate data not readily available for QI projects

at the start of the visit and there is real time decision support for PCPs (e.g., how to respond to a parent who thinks counseling is useless) vs. the Traditional paper-and-pencil approach. Selected documentation is sent to the child's EHR. In addition, SEEKonline provides aggregate data for needs assessments and QI projects. Nevertheless, some practices will choose the Traditional approach; they too will include SEEK-related information in a child's EHR (see Table 2).

**Summary.** Primary care offers an excellent opportunity to help address psychosocial problems, promote children's wellbeing, and help prevent CM by broadly implementing the SEEK model. The proposed study aims to use technology to facilitate the accessibility and implementation of SEEK and to evaluate its effectiveness in helping prevent CM. This fits well with NICHD's vision for translational research to promote sustainable behavioral change in the context of social factors, and "to transform this knowledge into effective interventions to improve health across different settings and populations."

## B. INNOVATION

This proposed study involves a rigorous hybrid III design to address both implementation and effectiveness aims, integrating knowledge from pediatric primary care, family medicine, CM prevention, implementation science and health economics, to examine how technology driven implementation strategies can enhance SEEK's scalability.

**Prevention in primary healthcare settings.** The proposed study will offer a new understanding of the barriers to and facilitators of the adoption and optimal implementation of SEEK, the only EBP for the prevention of CM developed for primary healthcare.

**Pediatric and family medicine primary care practices.** SEEK will be studied in both settings. This is important in that studies to date have only been in pediatric practices.

**The use of technology driven implementation strategies.** As medicine transitions to electronic approaches, this study will provide valuable information regarding online and distance learning as well as the SEEKonline web-based software, and how these influences PCPs' practice.

**Understanding PCPs', behavioral health professionals', office staffs' and parents' experiences implementing SEEK.** The study aims to understand participants' experiences regarding modalities developed to help implement the model, including the SEEK website, online training videos, and SEEKonline. In addition to quantitative measures, qualitative interviews with multiple groups of participants will be conducted to examine the effectiveness of different training and intervention strategies, in varied settings.

**Assessment of implementation process and associated costs within primary care settings.**

Although successfully implemented in our previous RCTs and 100 early adopting practices, there is much to be learned about the implementation process, costs and organizational factors that impact the SEEK's implementation in real-world settings. The Stages of Implementation Completion (SIC) provides an empirical way to characterize the implementation process. This framework enables a refined understanding of the implementation process and outcomes. The associated COINS (i.e., Cost of Implementing New Strategies) measures implementation costs. We will look at these implementation outcomes in relation to organizational factors such as leadership and climate—known correlates of implementation success. Finally, we will employ a mixed-methods design that integrates qualitative data from multiple groups of participants with quantitative data on intervention outcomes.

**A novel approach to tackling sensitive psychosocial problems.** Aside from post-partum depression, SEEK is one of few screens for social determinants of health based on evidence from pediatric settings.

**Guidance for dissemination and implementation strategies.** The above information should guide the development of new strategies to disseminate and implement evidence-based interventions such as SEEK in primary healthcare systems, and help build the knowledge base in IS. If successful, outcomes will be applicable to addressing social determinants of other child physical and behavioral health problems.

## C. APPROACH

### Preliminary Studies - Evidence from Two RCTs Supporting the Effectiveness of SEEK

Two federally-funded RCTs have been conducted on SEEK over the last 15 years.

**Studies' Aims.** There were 2 main aims: 1) to examine whether training in SEEK would significantly enhance PCPs' awareness, attitudes, level of comfort, perceived competence and practice behavior with regard to addressing the targeted risk factors (e.g., parental depression, substance abuse, food insecurity) for CM and 2) to examine whether SEEK would reduce the rate of CM, compared to standard pediatric primary care.

**Studies' Samples.** The SEEK I sample of 558 families was high risk, very low income, urban, mostly African American, and served by pediatric resident clinics in Baltimore, and involved 95 physicians. SEEK II involved 105 pediatricians and nurse practitioners and 1,119 relatively low risk, mostly white, middle-income families recruited from 18 suburban private pediatric practices in central Maryland.

**Studies' Design.** Practices in both studies were randomized to either SEEK or standard care. Following baseline evaluations of the PCPs, those randomized to SEEK received in-person training on how to address targeted risk factors for CM within a primary care visit. Parents were recruited from all practices with initial and follow-up assessments at 6 (SEEKI) or 12 (SEEK II) months. PCPs were evaluated at 18-36 months after the initial training. Toward the end of the studies, after 30-43 months (SEEK I and II), the children's medical records were reviewed for CM-related diagnoses, before and after implementing SEEK. Data were gathered from the state agency on possible Child Protective Services (CPS) involvement. We assessed parents' satisfaction with the child's PCP. In SEEK II, medical students observed PCPs during 3 checkups, at baseline and at study end, to observe their approach to and time spent on the targeted problems.

### Studies' Findings

**Impact on PCPs.** In both studies, PCPs in SEEK practices reported significantly greater comfort and perceived competence in addressing the targeted risk factors, compared to controls. Improvements were sustained for 18-36 months. Review of medical records revealed that PCPs in SEEK practices were significantly more likely than controls to screen for the targeted risk factors for CM. In SEEK II, this was confirmed by direct observation; screening increased on average across practices from less than 5% to 62% of visits. In SEEK I, parents in SEEK clinics reported more favorable views of their child's PCP. Importantly, busy PCPs demonstrated they could effectively implement SEEK.

**Impact on CM.** Three measures from three sources assessed CM: 1) parent self-report on the Conflict Tactics Scale, 2) review of children's medical records for abuse or neglect, and 3) CPS reports. *Parent self-report.* SEEK I parents reported fewer "severe physical assaults" than controls (0.11 vs. 0.33,  $p = .04$ ). SEEK II parents reported fewer instances of Psychological Aggression ( $p = .02$ ) and Minor Physical Assaults ( $p < .05$ ) than did controls. *Medical records.* Children in SEEK I practices had less medical neglect than did controls. There was less "non-compliance" with medical care (4.6% vs. 8.4%,  $p = 0.05$ ), and fewer delayed immunizations (3.3% vs. 9.6%,  $p = 0.002$ ). *CPS reports.* In SEEK I, fewer families were reported to CPS (12% vs. 19.7%,  $p = .04$ ). A report was prevented in one of every 13 such families exposed to SEEK.

**Time Required.** SEEK did not require significantly more time, on average, for PCPs to address psychosocial problems. Parents completing the PQ before visits saved time; this was offset when addressing problems.

**Cost.** SEEK II cost \$3.38 per child per year and \$210 per CM experience prevented. Using a conservative estimate of the healthcare cost per case of CM at \$2,908, providing SEEK in all practices would have saved society between 1.6 and 5 million dollars for 29,610 children. Thus, SEEK has a positive cost-benefit. However, it does not necessarily follow that practices can afford to implement SEEK. By focusing on implementation vs. intervention costs, the proposed study will evaluate the cost to a practice of implementing SEEK. Of note, CPT code 96161 enables PCPs to bill each time the SEEK Parent Questionnaire is administered.

### Strengths and Limitations of the Extant Research on SEEK

**Strengths.** Improvements in PCP thinking and practice regarding the targeted psychosocial problems to be known determinants of CM were sustained in both RCTs. Indeed, there was significantly less CM associated with SEEK - in both RCTs. Moreover, SEEK II demonstrated effectiveness in a sample that otherwise, would be considered to be relatively low risk, representing many American families, suggesting the potential for widespread benefit from scaling up SEEK.

**Limitations Addressed in the Proposed Research.** The studies did not probe what facilitated or challenged practices' and PCPs' adoption and implementation of SEEK. In addition, SEEK was only tested in

[figure not shown]
pediatric settings; there is a need to examine it in family medicine practices. Further, the labor-intensive in-person training used in the RCTs reduces the capacity for widespread scale-up. Evaluation of easily accessible methods for training and guidance in implementing SEEK including online training and SEEKonline decision support have the potential to increase adoption and implementation of SEEK with fidelity more broadly.

## Strategy and Design Overview (Figure 2).

The proposed study, based on SEEK I and II findings is designed to study the effectiveness of technology driven training strategies to facilitate use of SEEK in helping prevent CM and its adoption and implementation in pediatric and family medicine settings.

Implementation of EBPs may be even more challenging than their development and testing. This may apply especially to healthcare systems and preventive psychosocial interventions such as SEEK.

## Implementation framework: EPIS model.

The implementation approach is anchored in four stages of the EPIS conceptual model: Exploration, adoption/Preparation,

Implementation, and Sustainment. The strong evidence for SEEK's effectiveness has been underscored by its listing on the websites of the CDC, AHRQ, AAP, and by the California Clearinghouse for Evidence-Based Interventions in Child Welfare. Early adopters are increasingly implementing SEEK in primary care settings, including in Sweden. Four of the 5 healthcare systems in this proposal have implemented SEEK in some of their practices. However, practices within these systems operate independently of one another, and there should not be contamination among them. Each practice has its own lead physician, PCPs and administrative staff and several have integrated behavioral health. Given that early adopters are estimated to be 10% of those eligible and that medical innovations can take 17 years to be adopted, it is unlikely that SEEK's potential public health benefit will be realized without better methods for scaling up.

**Design.** The proposed implementation study is the first involving SEEK. We selected a rigorous Hybrid Type III design which is an approach to examine implementation outcomes while also examining SEEK's effectiveness in preventing CM, measured by EHR indicators. Type III designs are facilitated by good EHR systems due to the low cost of data routinely gathered for clinical, services, and financial purposes. This allows more resources to address the implementation outcomes of SEEK strategies in routine practice settings. In the past 4 years, over 80 papers reported use of hybrid designs. Practices will be randomized to one of the two training strategies (IND vs. MOC). Practices, however, will be able to select the facilitation strategy (SEEKonline or Traditional) as we are not able to require this of participants. The design accounts for heterogeneity in geography, size of healthcare systems, type of primary care (pediatric and family medicine), and presence of integrated behavioral health (see strong support letters from healthcare systems in Texas, Ohio, Utah, Wisconsin and North Carolina). As shown in Figure 2, professionals, office staff and parents are

nested within practices which are nested within the 5 healthcare systems. The participating systems will be randomized to one of two start times - 9 or 16 months from project start date, beginning with one pediatric and one family medicine system (cohort 1). Staggering the start time addresses the capacity limitations of the training and research staff.

**Sample.** We will offer SEEK to the 5 healthcare systems. Inclusionary criteria are: 1) practices not already implementing SEEK, 2) practices providing primary care to children, and 3) agreement to participate. The systems have indicated a general commitment to this project; they include 59 practices with 306 PCPs. Our recruitment efforts in SEEK II were very successful with 75% (18/24) of practices agreeing to participate, including all the PCPs in those practices. We plan to study 13 pediatric and 35 family medicine practices. If more practices are interested, we will select the first 48 choosing to participate. In the unlikely event that fewer than 48 are interested, we will approach other healthcare systems. In addition to 5 system leaders, we will recruit 5 groups of participants: 1) all 48 practice leaders, 2) 275 PCPs, 3) 16 behavioral health professionals, 4) 96 ancillary staff, and 5) 288 parents (6 per practice). These estimates are based on current staffing. Smaller subsamples will be purposively selected for qualitative interviews according to practice type, training strategy and presence of integrated behavioral health.

We will also request limited consent from practice leaders and PCPs who opt out to briefly probe their decision. We will ascertain aggregated ICD-10CM-related diagnoses on all children 0-5 attending the practices (N~90,000). Based on our experience, we anticipate 60% of practice leaders and PCPs will be female as will be most of the other participants. Different regions provide diversity in terms of urban, suburban and rural locations, and racial/ethnic diversity (e.g., 2 systems serve a predominantly Latino population). Three systems have integrated behavioral health professionals. These contextual factors will be considered in all analyses.

**Recruitment.** Leaders in the 5 healthcare systems will be approached to formally approve participation, without committing individual practices. A letter will be sent to physician leaders of practices inviting participation in the study. If interested, we will hold a 1-hour webinar with the practice leader, PCPs and behavioral health professionals together with key office staff. We will provide written material detailing what their involvement will entail. Participation will be voluntary, and, while we prefer that all the PCPs in a practice participate, this will not be required. We anticipate that behavioral health professionals and office staff will necessarily be involved in practices opting to participate. We will sign an MOU with participating practices, and request a limited informed consent by practice leaders and PCPs who opt out, to gather data regarding their decision and practice demographics. Informed consent will be obtained from all participants. This will be done online at the beginning of the first survey, an approach we used successfully in SEEK II. We will recruit one practice manager and nurse per practice. Finally, parents will be recruited via flyers describing the project in the waiting area. If interested, they will be asked to notify staff who will request their contact information and permission to convey their interest to SEEK project staff. We will contact them and explain the project by phone and in writing. Prior to the start of the first online survey, participant consent will be obtained.

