### **Child Maltreatment**

**EHR CM-related Diagnoses.** ICD-10 codes related to CM are readily accessible through EHRs. De-identified aggregate data will be gathered toward study end for all children 0-5 attending the practices during the study – for up to 2 years prior to and during the study.

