**Aim 3. Examine the effectiveness of SEEK in reducing CM.** As in our previous studies, we will identify CM-related diagnoses, now via EHRs. We will review the EHR for each child (0-5) in each practice for two years prior to implementing SEEK and during implementation. The presence of CM-related ICD-10 codes will be recorded. The proportion of children with CM diagnoses before and during SEEK will be compared at each practice. Formal inference regarding the best estimate and statistical significance of pre-post differences will be based on a binary regression model with a random effect for site, similarly to Aim 1.

**Sample Size Considerations.** Our projected sample sizes (numbers of practices, professionals within each practice, and children in the practices) should provide good precision to estimate parameters and ample power to detect moderate associations. Table 4 below shows the detectable effect sizes for various comparisons, based on performing 2-sided .05-level tests and incorporate a 1.5-fold increase in variance and sample size to account for potential loss of power due to clustering of observations within practices and systems. In general, the detectable effect sizes are moderate, at plausible levels. We observed effect sizes of about 1.0 regarding Competence and Comfort in SEEK II. For Aim 2, assuming 90% of practices provide organizational information, we will estimate the rate of adoption of SEEK accurately,  $\pm$  15 percentage points.

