**Table 4. Power Calculations**

Aim	Respondents/Source	Measure	N per group	Detectable Effects with 80% power
1a	PCPs	Changes in Comfort and Competence in addressing CM	137	Effect size  of 0.42
1a	Parents	Parent satisfaction	144	Effect size  of 0.41
1b	Staff	Staff Perceptions	24/72 	Effect size  of 0.82
2	Practices	Proportion adopting	59	Precision of +/- 15 pct points
3	EHR	Pre-post prevalence of CM-related diagnoses	98,000	5% vs. 4.5%  10% vs. 9.6%

Defined as the difference in means between groups divided by the standard deviation.

Conservatively assuming an imbalance between SEEKonline vs. Traditional of as much as 25% to 75%.

In our previous evaluations of SEEK, we observed rates of CM in the medical record ranging from 5% to 1%.

methods.

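### Table 4 sizes Aim 3 on 98,000 children per group while the Sample section counts about 90,000 with no time window; the two are not reconciled, and the printed 10% vs 9.6% is not supported at either count.

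*Combined protocol and SAP*

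**What the plan says.** Three places in the combined protocol and SAP bear on the number of children.

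- **Sample (C. Approach):** "We will ascertain aggregated ICD-10CM-related diagnoses on all children 0-5 attending the practices (N~90,000". The figure is approximate and carries no time window.
- **Table 4, Aim 3 row:** "Pre-post prevalence of CM-related diagnoses 98,000 5% vs. 4.5", with 10% vs 9.6% as a second pair. The column headings are "N per group Detectable Effects with 80% power".
- **Child Maltreatment measure:** "De-identified aggregate data will be gathered toward study end for all children 0-5 attending the practices during the study", reaching back up to two years before the study.

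The Aim 3 analysis is a before-and-during comparison: "The proportion of children with CM diagnoses before and during SEEK will be compared at each practice". In that setting the natural reading of N per group is children per period, although the table does not spell this out. Sample Size Considerations says that the table is "based on performing 2-sided .05-level tests" and that the calculations "incorporate a 1.5-fold increase in variance and sample size to account for potential loss of power due to clustering".

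**The concern.** The table's count is 98,000 / 90,000 = 1.089 times the Sample section's count, a gap of 8.9%. This looks like more than loose rounding, because every other N in Table 4 traces to the Sample section:

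- 137 per group is 275 PCPs halved (137.5).
- 144 per group is 288 parents halved.
- 24/72 is 96 ancillary staff split 25%/75%.
- 59 is the number of practices in the five systems.

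Only 98,000 has no source there. The Aim 3 row is the plan's only power statement for the child maltreatment outcome, so a reader needs to know what its N counts and whether the detectable differences follow from it.

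**Working it through.** **Inputs.** N per group 98,000 and the pairs 5% vs 4.5% and 10% vs 9.6% (Table 4); about 90,000 children (Sample); two-sided 0.05, 80% power and a 1.5-fold inflation (Sample Size Considerations and Table 4).

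**Formula.** Two-proportion normal approximation, periods treated as independent, effective n = N/1.5 per period:

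power = Φ[(d − 1.96·SE0)/SE1], where d = p1 − p2, SE0 = √(2·p̄(1−p̄)/n) and SE1 = √((p1(1−p1) + p2(1−p2))/n). For unequal periods, 1/n1 + 1/n2 replaces 2/n, with p̄ weighted by period size and each variance in SE1 divided by its own n.

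**How the 1.5 factor was used.** Applied once, it gives t-based effect sizes of 0.417, 0.406 and 0.822 for 137, 144 and 24/72. Table 4 prints 0.42, 0.41 and 0.82. So one application is the plan's own method for the other rows.

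**The plan's Aim 3 figures at 98,000** (n = 98,000/1.5 = 65,333):

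- 5% vs 4.5%: SE0 = 0.001177, SE1 = 0.001177; (0.005 − 0.002307)/0.001177 = 2.29; power 98.9%.
- 10% vs 9.6%: SE0 = 0.001645, SE1 = 0.001645; (0.004 − 0.003224)/0.001645 = 0.47; power 68.1%.
- Solving for 80% power gives 5% vs 4.67% and 10% vs 9.54%.

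Neither printed pair is reproduced, and no single variant tried gives both. Without inflation the pairs are 4.73% and 9.62%. With inflation but a one-sided test they are 4.70% and 9.59%. With 98,000 as the total (49,000 per period) they are 4.53% and 9.35%. For 80% power with the 1.5 factor, 5% vs 4.5% needs 42,612 per period and 10% vs 9.6% needs 130,089.

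**Readings of 90,000.** The documents do not choose between them. Two need assumptions of mine: a six-year age band, turnover by ageing only, a 2-year pre-window and a 32-month SEEK window (months 9 to 41 and 16 to 48). A panel of size P then yields P(1 + w/6) distinct children over w years.

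- *Current panel of 90,000:* 90,000(1 + 2/6) = 120,000 before and 90,000(1 + 2.667/6) = 130,000 during.
- *Distinct total over both windows:* P = 90,000/(1 + 4.667/6) = 50,625, giving 67,500 before and 73,125 during.
- *Crude floor:* 90,000 split into 45,000 and 45,000.

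| Children per period | Detectable from 5% | Detectable from 10% | Power 5% vs 4.5% | Power 10% vs 9.6% |
|---|---|---|---|---|
| 120,000 / 130,000 | 4.71% | 9.59% | 99.8% | 78.4% |
| 98,000 (Table 4) | 4.67% | 9.54% | 98.9% | 68.1% |
| 90,000 | 4.65% | 9.52% | 98.3% | 64.4% |
| 67,500 / 73,125 | 4.61% | 9.46% | 94.9% | 53.9% |
| 45,000 | 4.51% | 9.32% | 82.1% | 37.7% |

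**The case against.** The strongest reply is that the mismatch may be harmless. The Sample figure is approximate and undated. If it is a point-in-time panel, a multi-year window would hold more than 98,000 distinct children. The first printed pair is conservative on every line of the table above. The second pair starts from 10%, which lies above the 5% to 1% range of medical-record rates given in the footnote to Table 4, so it may matter less in practice.

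Most of this stands. In particular, a reader might infer that the plan cannot deliver 98,000 per period, or that the row overstates the study's sensitivity because its N is too high. The documents do not support either inference. The first needs 90,000 to be a per-period or study-wide count, which is nowhere stated. The second fails for 5% vs 4.5%, which holds at every count considered. For 10% vs 9.6%, the shortfall is already present at 98,000, so the gap between the two counts is not its cause.

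What does not fall away is that the plan gives two different child counts, defines neither by window, and prints a second detectable difference that its stated method does not yield at either count.

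**Conclusion.** The inconsistency is real, and its direction cannot be settled from the documents. Its own effect is minor: about 0.02 percentage points on the detectable rate between 98,000 and 90,000 per period, with power falling by 0.6 points for 5% vs 4.5% and by 3.7 points for 10% vs 9.6%. The 5% vs 4.5% statement is safe. The 10% vs 9.6% statement is not supported as printed at 98,000 or at 90,000, and needs correcting whichever count is adopted.

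These results rest on reading N per group as children per period, on the 1.5 factor applied once, and on treating the periods as independent. The turnover scenarios are illustrative. The origin of 98,000 is not given, and I do not assume one. This is a low-severity correction to the sizing table; it does not call the Aim 3 design into question.

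**What to change.** Use one defined child count in the Sample section and in Table 4. State the expected number of distinct children aged 0-5 in the 48 participating practices separately for the pre-SEEK window and the SEEK window, give the length of each window, and put both numbers in the Aim 3 row. Recompute both detectable differences from those counts with the 1.5 factor applied, as in the other rows.

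The cost is one count query to the systems' EHRs and a restated table row. At 90,000 per period the row would read 5% vs 4.65%, a smaller detectable difference than now printed, and 10% vs 9.52%, a slightly less favourable one. No change to design, data collection or analysis follows.
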